7. DETAILED STUDY PROCEDURES

7.1. Subject Identification

Subject numbers will be assigned sequentially to subjects consenting to participate in the study, according to the range of subject numbers allocated to each study centre.

7.2. General Study Aspects

Supplementary study conduct information not mandated to be present in this protocol is provided in the accompanying Study Procedures Manual (SPM). The SPM provides the investigator and the site personnel with administrative and detailed technical information that does not impact the safety of the subjects.

7.3. Outline of the Study Procedures**Table 2 List of study procedures**

Epoch	Prospective data collection			
	Visit 1	Visit 2	Visit 3 #	Visit 4 #
Time points	Day 1	Day 8	Day 29	Day 36
Type of contact	Study visit	Study visit or mailing*	Study visit	Study visit or mailing*
Country	Belgium, Germany, and Spain	Belgium, Germany, and Spain	Spain	Spain
Informed consent	•			
Check inclusion criteria	•			
Check exclusion criteria	•			
Collect demographic data	•			
Collect "at risk" status as per HCP assessment	•			
Record the vaccination data for GSK's quadrivalent seasonal influenza vaccine	•		•	
Check and record co-administered vaccination	•		•	
Distribute ADR cards	○		○	
Train subject/subject's parent (or LAR) to complete ADR cards	○		○	
Subject/subject's parent (or LAR) records post-vaccination AEs and/or other AEs occurring within 7 days post vaccination	•	•	•	•
Subject/subject's parent (or LAR) returns ADR cards *		○		○
Investigator or delegate transcribes data from ADR cards into the eCRF		•		•
Record of vaccine-related SAEs occurring within 7 days post vaccination	•	•	•	•
Study conclusion		•##		•

ADR card: adverse drug reaction card; AE: adverse event; AEI: adverse event of interest; eCRF: electronic case report form; HCP: healthcare professional; LAR: legally acceptable representative; SAE: serious adverse event

• is used to indicate a study procedure that requires documentation in the individual eCRF

○ is used to indicate a study procedure that does not require documentation in the individual eCRF

Only applicable for children aged <9 years who have not previously been vaccinated against influenza in preceding seasons and to whom a second dose should be given after an interval of at least 4 weeks and within the study period (see Table 3), and if the second dose of influenza vaccine is GSK's quadrivalent seasonal influenza vaccine.

Not applicable for children aged <9 years if they follow the recommendations of a 2-dose schedule with 4 weeks interval.

* Subject/subject's parent (or LAR) returns ADR cards either in person during a study visit or by mail, to the HCP (or a member of his/her team)

Whenever possible, the investigator should arrange study visits within the optimal intervals and no later than the allowed intervals ([Table 3](#)).

Table 3 Intervals between study visits

Interval	Optimal length of interval	Allowed interval
Visit 1 (Day 1) → Visit 2 (Day 8)	7 days	7 days – 14 days
Visit 1 (Day 1) → Visit 3 # (Day 29)	28 days	28 days – 42 days
Visit 3 # (Day 29) → Visit 4 # (Day 36)	7 days	7 days – 14 days

Only applicable for children aged <9 years who have not previously been vaccinated against influenza in preceding seasons and to whom a second dose should be given after an interval of at least 4 weeks and within the study period, and if the second dose of influenza vaccine is GSK's quadrivalent seasonal influenza vaccine.

7.4. Detailed Description of Study Procedures

7.4.1. Informed consent

The signed/witnessed/thumb printed informed consent of the subject/subject's parent(s)/LAR(s) must be obtained before study participation. The signed informed assent of a subject below the age of consent (i.e., minor) should be obtained in addition to the signed informed consent by his/her parent(s)/LAR(s) according to local rules and regulations. Refer to Section [6.1](#) for the requirements on how to obtain informed consent and assent, as appropriate.

7.4.2. Check inclusion and exclusion criteria

Check all applicable inclusion and exclusion criteria as described in Sections [5.2](#) and [5.3](#) before enrolment.

7.4.3. Collect demographic data

Record demographic data (including month and year of birth, gender and race) in the subject's eCRF.

7.4.4. Collect "at risk status"

Record the "risk status" (i.e., at risk/not at risk) for influenza-associated morbidity and mortality as per HCP assessment in the subject's eCRF.

The risk status should be defined by the HCP based on his/her judgment and experience. Risk groups usually recommended for seasonal influenza vaccination in the EU include but are not limited to:

- pregnant women
- individuals >6 months with chronic heart or lung diseases, metabolic or renal disease, chronic liver disease, chronic neurological conditions or immunodeficiencies
- residents of long-term care facilities for older persons and the disabled

- children aged 6–59 months
- healthcare workers including those who work in facilities that care for the elderly or persons with disabilities

7.4.5. Record vaccination data for GSK’s quadrivalent seasonal influenza vaccine

Record in the subject’s eCRF information on seasonal influenza vaccine, such as the date of administration and the batch number.

7.4.6. Check and record co-administered vaccination

Co-administered vaccination administered on the same day as the subject’s GSK’s quadrivalent seasonal influenza vaccine must be recorded in the eCRF.

7.4.7. ADR cards

Customized ADR cards will be used to collect the AEs and/or other AEs within 7 days post each vaccination (i.e., the day of vaccination and the following 6 days). After written informed consent/informed assent is obtained from the subject/the subject’s parent(s)/LAR, the ADR cards will be provided to the subjects/subjects’ parent’(s)/LAR on the day of vaccination. The subjects/subjects’ parent’(s)/LAR will be asked to complete the ADR cards with any AEs and/or other AEs occurring within 7 days post vaccination and to return the cards to the HCP at the next study visit or by mail. The investigator or delegate will transcribe the collected information into the eCRF database.

Note: ADR cards can be filled in by a minor subject under the supervision of the subject’s parent(s)/LAR(s) provided that the minor has the competence to assess and report the information to be provided on the ADR cards. The ultimate accountability for the completion of the ADR cards remains with the subject’s parent(s)/LAR(s). The investigator should discuss this accountability with the subject’s parent(s)/LAR(s).

7.4.8. Study conclusion

The investigator will:

- Review all the data collected to ensure accuracy and completeness.
- Complete the Study Conclusion screen in the eCRF.

7.5. Biological Sample Handling and Analysis

Not applicable.

8. SAFETY

The investigator or site staff is/are responsible for the detection, documentation and reporting of events meeting the criteria and definition of an AE of specific interest or an SAE as provided in this protocol.

Each subject/subject's parent(s)/ LAR(s) will be instructed to contact the investigator immediately should they/the subject manifest any signs or symptoms they perceive as serious/of concern or indicating a change in their health status.

8.1. Safety Definitions

8.1.1. Definition of an adverse event

An AE is any untoward medical occurrence in a subject, temporally associated with the use of a medicinal product, whether or not considered related to the medicinal product, or temporally associated with a study procedure.

An AE can therefore be any unfavourable and unintended sign (including an abnormal laboratory finding), symptom, or disease (new or exacerbated) temporally associated with the use of a medicinal product. For marketed medicinal products, this also includes failure to produce expected benefits (i.e., lack of efficacy), abuse or misuse.

8.1.2. Definition of a serious adverse event

An SAE is any untoward medical occurrence that:

- a. Results in death,
- b. Is life-threatening,

Note: The term 'life-threatening' in the definition of 'serious' refers to an event in which the subject was at risk of death at the time of the event. It does not refer to an event, which hypothetically might have caused death, had it been more severe.

- c. Requires hospitalisation or prolongation of an existing hospitalisation,

Note: In general, hospitalisation signifies that the subject has been admitted at the hospital or emergency ward for observation and/or treatment that would not have been appropriate in the physician's office or in an out-patient setting.

Complications that occur during hospitalisation are also considered AEs. If a complication prolongs hospitalisation or fulfils any other serious criteria, the event will also be considered serious. When in doubt as to whether 'hospitalisation' occurred or was necessary, the AE should be considered serious.

Hospitalisation for elective treatment of a pre-existing condition (known or diagnosed prior to informed consent signature) that did not worsen from baseline is NOT considered an SAE.

- d. Results in disability/incapacity,

Note: The term disability means a substantial disruption of a person's ability to conduct normal life functions. This definition is not intended to include experiences of relatively minor medical significance such as uncomplicated headache, nausea, vomiting, diarrhoea, influenza like illness, and accidental trauma (e.g., sprained ankle) which may interfere or prevent everyday life functions but do not constitute a substantial disruption.

or

- e. Is a congenital anomaly/birth defect in the offspring of a study subject.

Medical or scientific judgement should be exercised in deciding whether reporting is appropriate in other situations, such as important medical events that may not be immediately life-threatening or result in death or hospitalisation but may jeopardise the subject or may require medical or surgical intervention to prevent one of the other outcomes listed in the above definition. These should also be considered serious. Examples of such events are invasive or malignant cancers, intensive treatment in an emergency room or at home for allergic bronchospasm, blood dyscrasias or convulsions that do not result in hospitalisation.

8.1.3. Adverse events of specific interest

AEs that comprise the primary interest of the study are designated as AEs. Please refer to [APPENDIX C](#) for the pre-defined list of AEs.

8.2. Reporting of SAEs and Other Events

It will be clearly communicated to participating HCPs that the study does not replace reporting of AEs/SAEs that should occur as part of routine practice as specified by local regulations. It is not the intention of the surveillance to influence or change the usual local reporting processes. HCPs should continue to report any AEs/SAEs they would typically report using the mechanisms routinely used in their healthcare practice. Therefore, although the data collected for this study is primarily safety-related data, reporting mechanisms of AEs to regulatory authorities should not be altered and are to continue according to local standards.

If the participating HCP becomes aware of an SAE experienced by a study participant occurring within 7 days post vaccination that is deemed to be related to GSK's quadrivalent seasonal influenza vaccine according to the judgement of the HCP, the SAE should be reported to GSK within 24 hours of becoming of aware using the eCRF. This will be linked to the central safety database (Argus) with a study ID link mechanism therefore it is not necessary to report separately to central safety (GSK Biologicals Clinical Safety & Pharmacovigilance, e-mail: ^{PPD} using the GSK reporting forms) unless there are issues with access to the eCRF preventing the electronic reporting of the SAE within the required timeframe. If GSK deems additional information is necessary, request *for* additional information will be sent to the HCP.

9. SUBJECT COMPLETION AND WITHDRAWAL

9.1. Subject Completion

A subject who returns for the concluding visit foreseen in the protocol or has returned the completed ADR card is considered to have completed the study.

9.2. *Subject Withdrawal*

A subject who does not return for the concluding visit foreseen in the protocol or has not returned the completed ADR card will be considered a withdrawal from the study. If the subject informs the Investigator of the reason for withdrawal from the study, the reason for this will be entered into the electronic Case Report Form as detailed below:

- *Seasonal influenza vaccine-related Serious Adverse Event*
- *Protocol Violation (to be specified)*
- *Consent withdrawal, not due to an adverse event (to be specified if the information is available)*
- *Not willing/not able to participate in the visit*
- *Migrated/moved from the study area*
- *Lost to follow-up*
- *Sponsor study termination*
- *Other (please specify)*

10. STATISTICAL METHODS

10.1. Endpoints

10.1.1. Primary endpoint

- Occurrence of AEs and/or other AEs within 7 days post each GSK's quadrivalent seasonal influenza vaccination (i.e., the day of vaccination and the following 6 days) reported using ADR cards, according to MedDRA classification, by cumulative weeks (expected ISO weeks 40 to 52).

10.1.2. Secondary endpoints

- Occurrence of AEs and/or other AEs within 7 days post each GSK's quadrivalent seasonal influenza vaccination (i.e., the day of vaccination and the following 6 days) reported using ADR cards, according to MedDRA classification, each week (expected ISO weeks 40 to 52).
- Occurrence of AEs and/or other AEs within 7 days post each GSK's quadrivalent seasonal influenza vaccination (i.e., the day of vaccination and the following 6 days) reported using ADR cards, according to MedDRA classification, by cumulative weeks (expected ISO weeks 40 to 52).

10.2. Determination of Sample Size

Approximately 1000 subjects will be enrolled in this study.

Table 4 shows the probability to observe at least one AE, the exact 95% Confidence Intervals (CIs) for the percentage of vaccinated subjects with the AE and Relative Standard Error (RSE) for a range of scenarios in term of number of vaccinated subjects and true percentage of vaccinated subjects with the AE:

- With an overall sample size of 1000 vaccinated subjects (whole study period, all countries) and a true percentage of vaccinated subjects with the AE ranging from 1% to 10%, the corresponding probability to observe at least one vaccinated subject with the AE is >99% and the RSE ranges from 9.5% to 31.5%.
- With an overall sample size of 75 vaccinated subjects (by week, all countries) and a true percentage of vaccinated subjects with the AE ranging from 1% to 10%, the corresponding probability to observe at least one vaccinated subject with the AE ranges from 52.9% to >99% and the RSE ranges from 34.6% to 114.9%.

Table 5 shows the evolution by week of the cumulative probability to observe at least one AE, the exact 95% CI for the cumulative percentage of vaccinated subjects with the AE and RSE in the course of the study for an overall sample size of 1000 (all countries) and 333 (by country) vaccinated subjects and a true percentage of vaccinated subjects with the AE of 1%.

Table 4 Probability to observe at least one AE, exact 95% Confidence Intervals and Relative Standard Error according to number of vaccinated subjects and true percentage of vaccinated subjects with the AE

Number of vaccinated subjects	True percentage of vaccinated subjects with the AE (%)	Probability ^s to observe ≥1 vaccinated subject with the AE (%)	Number of vaccinated subjects with the AE	Exact 95% CI* on the percentage of vaccinated subjects with the AE		Associated relative standard error (%)
				Lower Limit	Upper limit	
1500 (whole study period, all countries)	10	>99	150	8.53	11.63	7.7
	8	>99	120	6.68	9.49	8.8
	6	>99	90	4.85	7.32	10.2
	4	>99	60	3.07	5.12	12.6
	2	>99	30	1.35	2.84	18.1
	1	>99	15	0.56	1.64	25.7
	0.5	>99	7.5	0.21	1.00	36.4
	0.1	77.7	1.5	0.01	0.43	81.6
1000 (whole study period, all countries)	10	>99	100	8.21	12.03	9.5
	8	>99	80	6.39	9.86	10.7
	6	>99	60	4.61	7.66	12.5
	4	>99	40	2.87	5.41	15.5
	2	>99	20	1.23	3.07	22.1
	1	>99	10	0.48	1.83	31.5
	0.5	>99	5	0.16	1.16	44.6
	0.1	63.2	1	0.00	0.56	99.9
75 (per week, all countries)	10	>99	7.5	4.27	19.12	34.6
	8	>99	6	2.99	16.60	39.2
	6	99.0	4.5	1.83	13.99	45.7
	4	95.3	3	0.83	11.25	56.6
	2	78.0	1.5	0.14	8.28	80.8
	1	52.9	0.75	0.01	6.65	114.9
500 (whole study period, by country)	10	>99	50	7.51	12.97	13.4
	8	>99	40	5.78	10.73	15.2
	6	>99	30	4.08	8.45	17.7
	4	>99	20	2.46	6.11	21.9
	2	>99	10	0.96	3.65	31.3
	1	>99	5	0.33	2.32	44.5
	0.5	91.8	2.5	0.08	1.59	63.1
	0.1	39.4	0.5	0.00	0.93	141.4
333 (whole study period, by country)	10	>99	33.3	7.00	13.74	16.4
	8	>99	26.6	5.32	11.45	18.6
	6	>99	20	3.70	9.12	21.7
	4	>99	13.3	2.17	6.70	26.8
	2	>99	6.7	0.79	4.15	38.4
	1	96.5	3.3	0.23	2.76	54.5
	0.5	81.2	1.7	0.04	1.99	77.3
	0.1	28.3	0.3	0.00	1.30	173.2
25 (per week, by country)	10	92.8	2.5	1.70	28.67	60.0
	8	87.6	2	0.98	26.03	67.8
	6	78.7	1.5	0.44	23.27	79.2
	4	64.0	1	0.10	20.35	98.0

Number of vaccinated subjects	True percentage of vaccinated subjects with the AE (%)	Probability [§] to observe ≥1 vaccinated subject with the AE (%)	Number of vaccinated subjects with the AE	Exact 95% CI* on the percentage of vaccinated subjects with the AE		Associated relative standard error (%)
				Lower Limit	Upper limit	
	2	39.7	0.5	0.00	17.21	140.0
	1	22.2	0.25	0.00	15.52	199.0

[§] Binomial distribution

* [Clopper, 1934]

Table 5 Cumulative probability to observe at least one AE, exact 95% Confidence Intervals and Relative Standard Error by week for a true percentage of subjects with the AE of 1%

Number of vaccinated subjects	ISO weeks	Cumulative number of vaccinated subjects	Cumulative probability [§] to observe ≥1 vaccinated subject with the AE (%)	Cumulative number of vaccinated subjects with the AE	Average percentage of vaccinated subjects with the AE (%)	Exact 95% CI* on the cumulative percentage of vaccinated subjects with the AE		Associated relative standard error (%)
						Lower Limit	Upper limit	
1000 (whole study period, all countries)	40-40	75	52.9	0	1.00	0.00	4.80	114.9
	40-41	150	77.9	1	1.00	0.02	3.66	81.2
	40-42	225	89.6	2	1.00	0.11	3.17	66.3
	40-43	300	95.1	3	1.00	0.21	2.89	57.4
	40-44	375	97.7	3	1.00	0.17	2.32	51.4
	40-45	450	98.9	4	1.00	0.24	2.26	46.9
	40-46	525	>99	5	1.00	0.31	2.21	43.4
	40-47	600	>99	6	1.00	0.37	2.16	40.6
	40-48	675	>99	6	1.00	0.33	1.92	38.3
	40-49	750	>99	7	1.00	0.38	1.91	36.3
	40-50	825	>99	8	1.00	0.42	1.90	34.6
	40-51	900	>99	9	1.00	0.46	1.89	33.2
	40-52	1000	>99	10	1.00	0.48	1.83	31.5
333 (whole study period, by country)	40-40	25	22.2	0	1.00	0.00	13.72	199.0
	40-41	50	39.5	0	1.00	0.00	7.11	140.7
	40-42	75	52.9	0	1.00	0.00	4.80	114.9
	40-43	100	63.4	1	1.00	0.03	5.45	99.5
	40-44	125	71.5	1	1.00	0.02	4.38	89.0
	40-45	150	77.9	1	1.00	0.02	3.66	81.2
	40-46	175	82.8	1	1.00	0.01	3.14	75.2
	40-47	200	86.6	2	1.00	0.12	3.57	70.4
	40-48	225	89.6	2	1.00	0.11	3.18	66.3
	40-49	250	91.9	2	1.00	0.10	2.86	62.9
	40-50	275	93.7	2	1.00	0.09	2.61	60.0
	40-51	300	95.1	3	1.00	0.21	2.89	57.4
	40-52	333	96.5	3	1.00	0.19	2.61	54.5

[§] Binomial distribution

* [Clopper, 1934]

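### Table 5 computes its exact confidence intervals from event counts rounded down but labels every row 1.00%, so 19 of 26 rows are inconsistent and four contradict Table 4

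*Protocol*

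**What the plan says.** Section 10.2 of the protocol has two planning tables. Table 4 covers a range of sample sizes and true percentages. Table 5 follows cumulative accrual over ISO weeks 40 to 52 and is introduced as showing "the exact 95% CI for the cumulative percentage of vaccinated subjects with the AE and RSE in the course of the study". It has two blocks, one building up to 1000 subjects across the three countries and one to 333 in a single country, and both assume that 1% truly have the event. Its title repeats that premise: "exact 95% Confidence Intervals and Relative Standard Error by week for a true percentage of subjects with the AE of 1" per cent. One column, headed "Average percentage of vaccinated subjects with the AE", holds 1.00 in all 26 rows. The interval columns are headed "Exact 95% CI* on the cumulative percentage of vaccinated subjects with the AE". The only notes under the table name the binomial distribution and cite Clopper-Pearson; rounding is not mentioned.

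The first overall row of Table 5 reads "40-40 75 52.9 0 1.00 0.00 4.80 114.9" (weeks, n, probability, count, average percentage, lower limit, upper limit, relative standard error). Table 4 at n = 75 and 1% reads "1 52.9 0.75 0.01 6.65 114.9" (true percentage, probability, count, lower limit, upper limit, relative standard error). Probability and relative standard error are identical in the two rows; the count and the interval are not.

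**The concern.** A planning row should describe one scenario. In most rows of Table 5 the probability and relative standard error describe a 1% event rate, while the interval describes a lower rate, 0% in the smallest samples, beside a printed 1.00. The reader also gets two different exact intervals for the same n and the same assumed rate from adjacent tables.

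Table 5 is the protocol's week-by-week statement of precision for cumulative percentages, which are the form of the primary endpoint. If the upper limits are understated, early-season precision looks better than it does on the convention of Table 4. Rounding down also makes the country-block upper limit rise at some steps as subjects accrue, which an expected-precision table should not show.

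**Working it through.** **Inputs.** All come from section 10.2: n and the event count for each row, the assumed 1%, and the exact (Clopper-Pearson) two-sided 95% method cited under both tables.

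**Formulas.**
- Lower limit = Beta(0.025; x, n − x + 1), taken as 0 when x = 0.
- Upper limit = Beta(0.975; x + 1, n − x). For x = 0 this reduces to 1 − 0.025^(1/n).
- Probability of at least one event = 1 − (1 − p)^n.
- Relative standard error = √[(1 − p)/(np)].

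**Step 1: reproduce Table 4.** With x = np left fractional (0.75 at n = 75, 0.25 at n = 25, 3.33 at n = 333), all 44 printed intervals are recovered to two decimals.

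**Step 2: reproduce Table 5.** All 26 printed counts equal 0.01 × n rounded down. Rounding to nearest would not give them: n = 75 would give 1, not 0, and n = 175 would give 2, not 1. The Clopper-Pearson limits for those counts match the print, except for two country-block upper limits that are 0.01 too high (n = 225: printed 3.18, computed 3.174; n = 275: printed 2.61, computed 2.602).

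Worked row, n = 75:
- Count: 0.01 × 75 = 0.75, printed as 0.
- Upper limit for 0/75: 1 − 0.025^(1/75) = 4.80%, as printed.
- Probability: 1 − 0.99^75 = 52.9%, as printed.
- Relative standard error: √(0.99/0.75) = 114.9%, as printed.

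The last two need p = 1%; the interval needs 0/75 = 0%.

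**Step 3: count the rows affected.** The product 0.01 × n is whole in 7 rows (overall n = 300, 600, 900, 1000; country n = 100, 200, 300). In the other 26 − 7 = 19 rows (9 overall, 10 by country) the interval belongs to a proportion below 1%. Examples are 0/75 = 0.00%, 1/175 = 0.57%, 3/375 = 0.80% and 8/825 = 0.97%.

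**Step 4: compare with Table 4 at the same n and 1%.** Five rows have a counterpart. Four differ; n = 1000 (0.48–1.83) agrees because its count is whole.

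| n | Table 5 | Table 4 |
|---|---|---|
| 75 (overall, week 40) | 0.00–4.80 | 0.01–6.65 |
| 75 (country, weeks 40–42) | 0.00–4.80 | 0.01–6.65 |
| 25 (country, week 40) | 0.00–13.72 | 0.00–15.52 |
| 333 (country, weeks 40–52) | 0.19–2.61 | 0.23–2.76 |

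**Step 5: recompute the 19 rows with x = 0.01 × n.** The 7 whole-count rows do not change.

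| Block | n | Printed | With x = 0.01 × n | Gap in upper limit (points) |
|---|---|---|---|---|
| Overall | 75 | 0.00–4.80 | 0.01–6.65 | 1.85 |
| Overall | 150 | 0.02–3.66 | 0.07–4.21 | 0.55 |
| Overall | 225 | 0.11–3.17 | 0.14–3.35 | 0.18 |
| Overall | 375 | 0.17–2.32 | 0.26–2.61 | 0.29 |
| Overall | 450 | 0.24–2.26 | 0.30–2.42 | 0.16 |
| Overall | 525 | 0.31–2.21 | 0.34–2.27 | 0.06 |
| Overall | 675 | 0.33–1.92 | 0.39–2.08 | 0.16 |
| Overall | 750 | 0.38–1.91 | 0.42–2.00 | 0.09 |
| Overall | 825 | 0.42–1.90 | 0.44–1.94 | 0.04 |
| Country | 25 | 0.00–13.72 | 0.00–15.52 | 1.80 |
| Country | 50 | 0.00–7.11 | 0.00–8.97 | 1.86 |
| Country | 75 | 0.00–4.80 | 0.01–6.65 | 1.85 |
| Country | 125 | 0.02–4.38 | 0.05–4.71 | 0.33 |
| Country | 150 | 0.02–3.66 | 0.07–4.21 | 0.55 |
| Country | 175 | 0.01–3.14 | 0.10–3.84 | 0.70 |
| Country | 225 | 0.11–3.18 | 0.14–3.35 | 0.17 |
| Country | 250 | 0.10–2.86 | 0.17–3.17 | 0.31 |
| Country | 275 | 0.09–2.61 | 0.19–3.02 | 0.41 |
| Country | 333 | 0.19–2.61 | 0.23–2.76 | 0.15 |

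The lower limits also sit low, by 0.01 to 0.10 points, except at n = 25 and n = 50, where two decimals show no change.

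**Step 6: non-monotone limits.** In the country block the printed upper limit rises from 4.80 (n = 75) to 5.45 (n = 100), from 3.14 (n = 175) to 3.57 (n = 200), and from 2.61 (n = 275) to 2.89 (n = 300). With x = 0.01 × n it falls at each of these steps (6.65 to 5.45, 3.84 to 3.57, 3.02 to 2.89).

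**The case against.** The best defence is that Table 5 prints the whole count beside each interval, and the interval is right for that count apart from two slips of 0.01. The 1.00 column can be read as the assumed rate rather than the observed proportion, so the fault would be an unstated rounding rule and not 19 wrong percentages. Whole counts are also what a study can observe; Table 4's intervals for 0.75 or 0.25 events interpolate the formula and are not exact intervals for any possible outcome. Finally, nothing rests on these limits: the section's text cites only probabilities and relative standard errors, all analyses are descriptive, and the interval method for the analysis is deferred to the SAP.

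Much of this stands. Calling the upper limits too low is relative to Table 4's convention, and 15 of the 19 rows have no Table 4 counterpart to contradict. The early intervals are wide under either convention, and from n = 450 in the overall block no gap exceeds 0.16 points. But reading 1.00 as the assumed rate does not explain why the interval in the same row rests on another rate, or why Table 4 gives a different interval for the same scenario. The section uses two conventions and states neither.

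**Conclusion.** The point holds; its consequence is small. Table 5 mixes an unrounded 1% (probability, relative standard error, label) with a rounded-down count (interval) in 19 of 26 rows, and four rows contradict Table 4 outright. Taking Table 4's convention as the reference, the upper limits are understated by 0.04 points (n = 825) to 1.86 points (n = 50). The three smallest samples, n = 25, 50 and 75, are each off by 1.80 points or more. Without choosing a reference, what remains is the contradiction between the tables and the mismatch within rows. The two upper limits for n = 225 with count 2 (3.17 and 3.18) are a separate and trivial slip.

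The sample size, the n = 1000 row, every probability and relative standard error, and the planned analyses stand as they are. The table should be corrected because its stated precision is inconsistent as written, not because the design is at risk.

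**What to change.** Use one convention and say which. Either of these resolves it:

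1. Recompute the count and interval columns of Table 5 with x = 0.01 × n, as Table 4 does, so that the tables agree at n = 25, 75, 333 and 1000. The replacement values are in the second table above. The stated precision becomes slightly less favourable.
2. Keep the whole counts and their intervals, replace 1.00 with the actual x/n in each row, and add a note that the expected count was rounded down. That note should also say why the intervals differ from Table 4, which uses unrounded counts.

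In either case give n = 225 the same upper limit in both blocks. If whole counts are kept, both should read 3.17, and the country-block limit at n = 275 should read 2.60. The cost is two or three columns of one table, or one column and a footnote, with no change to design, sample size or analysis.
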